5.9 Analyses of PK Parameters

Analysis of the PK parameters will be done using software SAS Version 9.4.

Subjects who did not keep identical insulin lispro doses for LY900014 and Humalog[®] for each day and period will be excluded from the statistical analysis of the PK parameters. Additionally, subjects which required a rescue insulin dose during the treatment assessment period would be excluded in the analysis for both treatments (LY900014 and Humalog) periods for that day (missed bolus following meal or basal insulin suspension) since an accurate comparison of the treatment difference would not be possible.

Log-transformed AUCs and C_{max} for insulin lispro will be evaluated to estimate geometric means, ratios of geometric means of insulin lispro within LY900014 to Humalog[®], and their corresponding 95% CIs of the ratios using the mixed-effects model that includes treatment (LY900014, Humalog[®]), period and sequence as fixed effects and subject within sequence as a random effect.

The same model without log transformation will be used for the analysis of the PK time parameters (time to early half-maximal drug concentration [early 50% t_{max}], and time of C_{max} [t_{max}], [late 50% t_{max} if calculated]). LS-means, treatment differences in LS-means, and the corresponding 95% CIs for the treatment differences will be estimated from the model. The p-value on the difference between LS-means will be used to determine statistical significance. The treatment ratios and 95% CIs for the ratios will be calculated using Fieller's theorem [4].

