In the evening of Day -1, subjects will receive a pre-defined evening meal. The subjects will cover the meal with a bolus administered by the study insulin pump. Overnight, the basal insulin infusion rate will be running and a target fasting plasma glucose level in the range of 126 ± 20 mg/dL will be aimed for. A single hourly basal rate will be started from at least – 3 hours prior to meal ingestion. At approx. 08:00 hours on Day 1, a standard liquid meal **CCI** will be provided. No bolus insulin will be administered with the aim to induce postprandial hyperglycemia ($PG > 240$ mg/dL). On-site glucose measurements **CCI** will be performed regularly and frequently after meal ingestion. As soon as a glucose measurement above the high glucose threshold ($PG > 240$ mg/dL) has been measured and the result has been confirmed by a second measurement, a correction bolus will be administered with the aim to bring the subject's glucose level down to $PG \leq 140$ mg/dL. Regular and frequent sampling for glucose on-site analysis continues and the time to reach the euglycemic range threshold will be documented. PK and glucose measurements will be collected until 5 hours after administration of the correction bolus. In case $PG < 54$ mg/dL, hypoglycemia rescue will be provided. In case $PG > 306$ mg/dL for more than one hour, hyperglycaemia rescue will be provided. Thereafter, subjects will receive a free-choice lunch and a pre-defined evening meal covered by the subject's usual bolus dose.

Day 1 / Day 2: recovery from hyperglycemia after basal insulin suspension

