	15 min	Glucose measurement: every 15 minutes If PG ≤ 200 mg/dL and every 5 minutes If PG > 200 mg/dL Insulin PK measurement: every 15 min	X	X	Ketones, every 30 min
	B ³	Confirmatory glucose measurement if PG > 240 mg/dL followed by IMP correction bolus with a syringe	X ⁴	X	Ketones ⁵
	B + 5min	As soon as PG ≤ 140 mg/dL is measured, a confirmatory PG is performed	X	X	
	B + 10min		X	X	
	B + 15min		X	X	
	B + 20min		X	X	
	B + 25min		X	X	
	B + 30min		X	X	Ketones
	B + 35min		X	X	
	B + 40min		X	X	
	B + 45min		X	X	
	B + 50min		X	X	
	B + 55min		X	X	
	B + 1h		X	X	Ketones
	B + 65min			X	
	B + 70min		X	X	
	B + 75min			X	
	B + 80min			X	
	B + 85min			X	
	B + 90min		X	X	Ketones
	B + 95min			X	
	B + 100min			X	

Clinical Trial Protocol				
Trial ID	EudraCT-No.	Date	Status / Version-No.	Page
I8B-MC-ITST	2019-003493-13	17 Jan 2020	Final 2.0	21 of 74

Approx. hour	Nominal timing	Activity	Insulin (PK)	Plasma glucose ¹	Other ²
	B + 105min		X	X	
	B + 110min			X	
	B + 115min			X	
	B + 2h	
If PG >180 mg/dL: Give additional correction bolus
 
If PG > 140 mg/dL, PG sampling will continue every 5 minutes
 
If PG ≤ 140 mg/dL, PG sampling will be every 15 minutes
	X	X	Ketones
	(B + 125 min)	If PG > 140 mg/dL		(X)	
	(B + 130min)	If PG > 140 mg/dL		(X)	
	B + 135min		X	X	
	(B + 140min)	If PG > 140 mg/dL		(X)	
	(B + 145min)	If PG > 140 mg/dL		(X)	
	B + 150min		X	X	Ketones
	(B + 155min)	If PG > 140 mg/dL		(X)	
	(B + 160min)	If PG > 140 mg/dL		(X)	
	B + 165min		X	X	
	(B + 170min)	If PG > 140 mg/dL		(X)	
	(B + 175min)	If PG > 140 mg/dL		(X)	
	B + 3h		X	X	Ketones
	(B + 185min)	If PG > 140 mg/dL		(X)	
	(B + 190min)	If PG > 140 mg/dL		(X)	
	B + 195min		X	X	
	(B + 200min)	If PG > 140 mg/dL		(X)	
	(B + 205min)	If PG > 140 mg/dL		(X)	
	B + 210min		X	X	Ketones
	(B + 215min)	If PG > 140 mg/dL		(X)	
	(B + 220min)	If PG > 140 mg/dL		(X)	
	B + 225min		X	X	
	B + 230min	If PG > 140 mg/dL		(X)	
	B + 235min	If PG > 140 mg/dL		(X)	
	B + 4h		X	X	Ketones
	(B + 245min)	If PG > 140 mg/dL		(X)	
	(B + 250min)	If PG > 140 mg/dL		(X)	
	B + 255min		X	X	
	(B + 260min)	If PG > 140 mg/dL		(X)	
	(B + 265min)	If PG > 140 mg/dL		(X)	
	B + 270 min		X	X	Ketones
	(B + 275min)	If PG > 140 mg/dL		(X)	
	(B + 280min)	If PG > 140 mg/dL		(X)	
	B + 285min		X	X	
	(B + 290min)	If PG > 140 mg/dL		(X)	
	(B + 295min)	If PG > 140 mg/dL		(X)	
	B + 5h	
End of experiment
 
Subject resumes usual pump therapy with own insulin pump.
 
Subject receives lunch
	X	X	Ketones

Clinical Trial Protocol				

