3.1 Background Information on Investigational Medicinal Products (IMPs)

3.1.1 Insulin lispro

The insulin analog insulin lispro (Humalog[®]) has been shown to be absorbed more quickly than regular human insulin (Humalog[®] package insert, 2015). In healthy volunteers given subcutaneous (SC) doses of insulin lispro ranging from 0.1 to 0.4 units (U)/kg, peak serum levels were seen 30 to 90 minutes after dosing (Humalog[®] package insert, 2015). However, the general consensus is that rapid-acting insulin is still not rapid enough to match carbohydrate absorption profiles, which limits efficacy and dosing flexibility. An ultra-rapid-acting prandial insulin would shift the PK/GD of insulin analogs so that they have an even faster onset to better match carbohydrate absorption and also allow greater flexibility in the time of dosing relative to meals.

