4.2 Endpoints

4.2.1 Primary endpoints:

- Time to recovery from hyperglycemia (time of correction bolus to time when PG = 140 mg/dL)

4.2.2 Secondary endpoints:

PD endpoints:

- $AUC_{(B-tPG140)}$, area under the PG curve but above 140 mg/dL from time of correction bolus (B) to time when PG is 140 mg/dL)
- $AUC_{(B-tPG180)}$, area under the PG curve but above 180 mg/dL from time of correction bolus (B) to time when PG is 180 mg/dL)
- Rate of change in PG (the change in PG at the time of bolus IMP administration to PG = 140 mg/dL measurement divided by the duration of time for this interval)
- PG_{max} , maximum observed plasma glucose

Clinical Trial Protocol				
Trial ID	EudraCT-No.	Date	Status / Version-No.	Page
I8B-MC-ITST	2019-003493-13	17 Jan 2020	Final 2.0	26 of 74

PK endpoint:

- t_{max} , time to maximum observed insulin concentration.
- Early 50% t_{max} , time to half-maximum before C_{max} .
- $AUC_{(0-15min)}$, are under the insulin curve from 0 to 15 minutes.
- $AUC_{(0-30min)}$, are under the insulin curve from 0 to 30 minutes.

4.2.3 Exploratory endpoints:

- Time to hyperglycaemia (PG > 240 mg/dL) after basal insulin suspension
- Peak ketone concentration after basal insulin suspension

4.2.4 Safety endpoints:

- Adverse Events

Further endpoints are defined in Section 13 and may be defined in the Statistical analysis plan (SAP).

Clinical Trial Protocol				
Trial ID	EudraCT-No.	Date	Status / Version-No.	Page
I8B-MC-ITST	2019-003493-13	17 Jan 2020	Final 2.0	27 of 74

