The PG must be kept within a range of 126 ± 20 mg/dL the last 30 min prior to start of meal intake. The PG level must not exceed each target range for more than 5 min, otherwise the run-in period should be adequately extended in order to fulfil the target ranges. Start of meal intake on Day 1 should start between 8:00 to 10:00 hours (8:00 preferred). Basal insulin suspension on Day 2 should start approx. 8-10 hours after the dinner meal on Day 1. The PG level prior to the start of the meal test and basal insulin suspension procedure during treatment period 2 should be similar to that of treatment period 1, if feasible.

Procedures in case of hypoglycaemia and hyperglycaemia during missed meal bolus and basal insulin suspension procedures

In case subject's plasma glucose concentration falls below 54 mg/dL (3.0 mmol/L, level 2 hypoglycaemia), the subject must be treated with either oral administration of rapidly absorbable carbohydrates or i.v. glucose as judged by the investigator to stop the hypoglycaemic episode

Clinical Trial Protocol				
Trial ID	EudraCT-No.	Date	Status / Version-No.	Page
I8B-MC-ITST	2019-003493-13	17 Jan 2020	Final 2.0	44 of 74

and the experimental procedure will be terminated. Date and time of termination (i.e., the start time of any treatment given for this hypoglycaemic episode) will be documented in the CRF. Hypoglycaemia with plasma glucose concentrations below 70 mg/dL (level 1) should not be treated until the completion of the meal test unless hypoglycaemic related symptoms are unacceptable for the subject.

In case subject's plasma glucose concentration rises above 306 mg/dL for more than 1 hour after correction bolus administration, or if the investigator deems it necessary, the subject will be treated with an additional bolus of the IMP (subcutaneously) at discretion of the investigator. The time of administration and amount of additional bolus will be documented in the CRF.

In both cases, blood samples for PK analysis will still be taken as planned.

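### SAP 5.9 drops rescued subject-days from every PK model, but its reason does not apply to AUC(0-15min) and AUC(0-30min) when the extra insulin came after those windows closed

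*SAP*

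**What the plan says.** SAP section 5.9 first excludes subjects whose insulin lispro doses differed between treatments. It then adds that "subjects which required a rescue insulin dose during the treatment assessment period would be excluded in the analysis for both treatments" for the day concerned, "since an accurate comparison of the treatment difference would not be possible". The rule covers the AUCs, Cmax and the time parameters alike and takes no account of when the extra insulin was given. The SAP defines neither the rescue dose nor the assessment period.

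Protocol section 4.2.2 names four PK endpoints: tmax, early 50% tmax and two partial AUCs. The first AUC is defined as "are under the insulin curve from 0 to 15 minutes" (sic), and the second runs to 30 minutes.

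The protocol describes extra insulin in three places:
- Section 8.8.1: an additional IMP bolus if plasma glucose (PG) "rises above 306 mg/dL for more than 1 hour after correction bolus administration, or if the investigator deems it necessary".
- Synopsis: PG above 306 mg/dL "for more than one hour, hyperglycaemia rescue will be provided", without saying that the hour starts at the bolus.
- Table 3 (Day 2), row B+2h: "If PG >180 mg/dL: Give additional correction bolus". Sections 8.8.1 and 8.8.3 do not mention this bolus.

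Section 8.8.1 also has the time and amount of any additional bolus entered in the CRF, and it continues PK sampling afterwards.

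Protocol section 13.4.3 excludes subjects from the PK analysis only for non-identical doses. SAP section 9 lists one change from the protocol, and it is not the rescue exclusion.

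**The concern.** The SAP's stated reason is that extra insulin spoils the treatment comparison. That is true of a parameter whose value the extra dose can change. It is not true of a partial AUC whose last sample was drawn before the extra dose was given, because a later dose cannot alter a concentration already measured.

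Two things are at stake. The first is precision: each rescued subject-day costs a complete within-subject pair, and the early-exposure AUCs bear directly on the secondary PK objective for a formulation described in Protocol section 3 as having increased early absorption. The second is selection: whether a subject counts in an analysis of the first 15 or 30 minutes depends on glucose an hour or more later, which may itself be related to absorption.

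**Working it through.** The plan gives no rescue rate and no figure for the effect of this exclusion, so there is no figure of its own to reproduce. The check has three parts.

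**1. Timing.** Inputs: endpoint windows from Protocol 4.2.2; PK samples every 5 minutes from B+5 to B+60 (Tables 2 and 3); baseline from two samples taken before the bolus (SAP 4.2); triggers from Protocol 8.8.1, the synopsis and Table 3.

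| Trigger | Earliest time | After AUC(0-15min) closes | After AUC(0-30min) closes |
|---|---|---|---|
| PG above 306 mg/dL for more than 1 h after bolus | about B+60 | 60 − 15 = 45 min | 60 − 30 = 30 min |
| Day 2 bolus, PG above 180 mg/dL | B+120 | 120 − 15 = 105 min | 120 − 30 = 90 min |
| Investigator judgement | not stated | unknown | unknown |

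The synopsis does not tie the hour to the bolus. For that version to act by B+30, PG would need to have been above 306 mg/dL for more than 60 − 30 = 30 minutes before the bolus. The bolus is given at the first confirmed value above 240 mg/dL, with sampling every 5 minutes once PG exceeds 200 mg/dL, so this is implausible.

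Both AUCs, including their baseline correction, are therefore fixed before either timed trigger can act. Only the discretionary bolus could fall inside a window, and its recorded time shows whether it did.

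**2. Which other parameters are safe.** Early 50% tmax is the time to half of Cmax, so it depends on Cmax. For insulin lispro in healthy volunteers, "peak serum levels were seen 30 to 90 minutes after dosing" (Protocol 3.1.1), a range that extends past B+60. As an illustration, take one-compartment curves with equal absorption and elimination rates (an assumption) and add a second dose half the size of the first:

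| tmax without second dose | Early 50% tmax without | Second dose at 61 min | Second dose at 120 min |
|---|---|---|---|
| 30 min | 7 min | 7 min | 7 min |
| 45 min | 10.5 min | 13.5 min | 10.5 min |
| 60 min | 14 min | 21 min | 14 min |
| 90 min | 21 min | 34.5 min | 27.5 min |

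In every scenario the ratio of AUC(0-30min) with and without the second dose is 1.000. Early 50% tmax can move, so it does not belong with the two AUCs.

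**3. Cost in precision.** Inputs: 24 completers (Protocol 13.1); two-sided 95% intervals (Protocol 13.2, SAP 5.5.2); k subjects excluded on a given day, assumed. In the 2×2 crossover, with sequences roughly balanced, the standard error of the treatment contrast is proportional to 1/√n, with n − 2 degrees of freedom.

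- SE ratio = √(24/(24 − k))
- 95% CI half-width ratio = [t(0.975, 22 − k)/√(24 − k)] ÷ [t(0.975, 22)/√24]

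| k (assumed) | n left | SE ratio | Half-width ratio |
|---|---|---|---|
| 2 | 22 | √(24/22) = 1.04 | 1.051 |
| 4 | 20 | √(24/20) = 1.10 | 1.110 |
| 6 | 18 | √(24/18) = 1.15 | 1.180 |
| 8 | 16 | √(24/16) = 1.22 | 1.267 |

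For the AUCs these ratios apply on the log scale. Under a time-based rule, neither timed trigger would remove any subject-day from the two AUCs.

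**The case against.** The best defence is consistency. SAP 5.7 applies the same rescue exclusion to the primary endpoint, and the secondary objective is framed as PK and PD during recovery, so one rule keeps the populations aligned. This is a reasonable preference, but it is not the reason the SAP gives, and that reason does not hold for the two AUCs.

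Several other points stand and limit the conclusion:
- A reader might infer that no extra insulin can be given before B+30. The discretion clause in 8.8.1 has no earliest time, so the documents do not support that.
- A reader might want to treat early 50% tmax as safe too, or to keep it with Cmax and tmax whenever a peak was seen before the extra dose. The first fails because of the dependence on Cmax. The second would make inclusion depend on the outcome: slow profiles would be dropped preferentially, and a faster formulation would pass more often. For these parameters a fixed pair exclusion is defensible.
- The data are not lost altogether. SAP 5.1 and 5.5.1 keep all subjects in listings and individual profiles, and SAP 5.2 allows, but does not require, a sensitivity analysis. The loss is from the models and from the summaries that 5.5.1 aligns with them.
- Changing the rescue sentence alone might achieve nothing. Rescue under 8.8.1 is more IMP, so the identical-dose sentence in SAP 5.9 and the same-dose condition in the mFAS (SAP 5.1) could still exclude these subjects. Protocol 5.4 speaks of identical correction bolus doses, which permits a narrower reading, but the SAP does not say so.

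**Conclusion.** The point holds for AUC(0-15min) and AUC(0-30min) only, and only when the recorded time of the extra dose is after B+15 or B+30 respectively. Both timed triggers satisfy that condition; a discretionary bolus has to be checked case by case. In those cases the exclusion removes unaffected pairs and makes the early-PK population depend on later glucose response.

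The size is unknown because the documents give no rescue rate. The SE increases of 4% to 22% (CI half-width 5% to 27%) for 2 to 8 exclusions are illustrations. The plausible number depends heavily on whether the Day 2 bolus at B+2h counts as rescue, which the SAP leaves open. Nor do the documents support saying that the resulting ratio is biased in a known direction; the selection is a feature of the rule, and its effect cannot be judged from them.

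These are secondary endpoints in a phase I trial. The change is worth making because it is cheap and the SAP's reason does not cover these endpoints; the primary analysis is not affected.

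**What to change.** In the SAP:

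1. Section 5.9: for AUC(0-15min) and AUC(0-30min), keep the subject-day when the CRF time of the extra dose, in each rescued period, is after the end of that window; otherwise exclude it. Judge each AUC against its own window.
2. Section 5.9: leave the pair exclusion in place for Cmax, tmax, early and late 50% tmax, AUC(0-300min) and AUC(0-∞).
3. Sections 5.9 and 5.1: state that, for these two AUCs, the identical-dose and same-dose conditions refer to the correction bolus, so that a later rescue dose does not exclude the same subjects by another route.
4. Define which doses count as rescue for analysis, and say whether the Day 2 bolus at B+2h is one of them. This concerns the analysis only; it takes no view on when extra insulin should be given.
5. Section 9: list the rescue exclusion as a change, since Protocol 13.4.3 does not contain it.

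The cost is SAP wording and one programming condition on a time already recorded, with no new samples. The drawback is that N will differ between the two early AUCs and the other PK parameters, and the early-PK population will no longer match the primary PD population. A table footnote should state both.

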5.10 Analyses of Safety Parameters

Safety endpoints will be presented for all subjects in the safety analysis set (SFAS).

Safety of the treatment will be evaluated by AEs, hypoglycaemic events, laboratory tests, vital signs, ECG and physical examination.

Safety results will be presented using descriptive statistics by visit/treatment and in subject data listings. In addition, listings of abnormal data will be presented.

Statistical Analysis Plan				
Trial ID	EudraCT-No.	Date	Status / Version-No.	Page
I8B-MC-ITST	2019-003493-13	15 Jul 2020	Final 1.0	33 of 47

5.10.1 Analysis of Adverse Events

All AEs will be presented by individual listings and non-hypoglycaemic TEAEs (TEAEs in this section are non-hypoglycaemic; severe hypoglycaemia will be taken in account) will be presented using summary tables by treatment. The following summary tables will be presented:

(1) Overview of Incidence of TEAEs including:

- Number of subjects at risk
- Incidence and number of TEAEs
- Incidence of deaths
- Incidence and number of serious TEAEs
- Incidence and number of other significant TEAEs
- Incidence and number of severe TEAEs
- Incidence and number of drug related TEAEs (possibly or probably related to IMP as judged by the investigator)

The presentation will be done by treatment.

(2) TEAEs by MedDRA system organ class (SOC) and preferred term within each SOC and preferred term as well as in total including incidence and number of TEAEs. The presentation will be done by treatment. SOC and preferred terms will be presented in alphabetic order.

(3) TEAEs by SOC and preferred term and by severity, relationship, seriousness, outcome, action taken with study drug due to this TEAE and other action due to this TEAE. The presentation will be done by treatment. SOC and preferred terms will be presented in alphabetic order. Within each category the presentation will be done from the lowest to the highest subcategory.

(4) Separate tables for SAEs (in case of more than 2 SAEs).

The incidence of TEAEs will be presented with the number and percentage of participants affected. Percentages will be derived as ratio of number of participants affected and number of participants at risk multiplied by 100.

The following will be included in the listing of AEs:

- Screening and randomisation number
- Gender, age, race and weight

Statistical Analysis Plan				
Trial ID	EudraCT-No.	Date	Status / Version-No.	Page
I8B-MC-ITST	2019-003493-13	15 Jul 2020	Final 1.0	34 of 47

- Event number
- Treatment
- SOC and PT term
- Event term
- Start date and time
- End date and time
- Last dose date and time
- Seriousness
- Severity
- Outcome
- Relationship to IMP
- Relationship to study device
- Action taken with study drug due to this AE
- Action taken with device
- Other action taken due to this AE
- Time since last dosing and duration

Two AE listings will be presented, one including all AEs that occurred during the trial and one including only death, serious, other serious and other significant AEs (incl AEs that lead to discontinuation). The AE listing including all AEs does not contain AEs related to hypoglycemic events. These will be presented separately (see Section 5.10.2). AESIs (hepatic events) will be listed separately, if they will occur.

5.10.2 Analysis of Hypoglycaemic Events

Hypoglycaemic events will be presented for all subjects in the SFAS by individual listings, and summary tables.

The following summary tables of hypoglycaemic events will be presented:

- Hypoglycaemic events total and within each classification as given in Section 4.6, separated by type of the episode, outcome, treatment and treatment administration.
- Separate tables will be presented for severe and non-severe hypoglycaemic events, if there are more than two severe hypoglycaemic events (Level 3).
- All presentations will be done by treatment/visit.

Statistical Analysis Plan				
Trial ID	EudraCT-No.	Date	Status / Version-No.	Page
I8B-MC-ITST	2019-003493-13	15 Jul 2020	Final 1.0	35 of 47

The incidence of hypoglycaemic events will be presented with the number and percentage of participants affected. Percentages will be derived as ratio of number of participants affected and number of participants at risk multiplied by 100.

The following will be included in the overall listing of AEs related to hypoglycaemic events:

- Screening and randomisation number
- Gender, age, race and weight
- Event number
- Treatment/Visit
- Classification (Level 1-3,)
- Type of hypoglycaemic episode
- Nocturnal hypoglycaemia
- Start date and time
- End date and time
- Last dose date and time
- Time since last dosing and duration of the episode
- Lowest glucose level during the episode, if available (incl specimen)
- Outcome
- Treatment (incl time of treatment)
- Glucose level before treating the episode, if available (incl specimen)
- Treatment administration (self, capable self, not capable self)
- Other treatment actions

A separate listing of severe hypoglycaemic episodes (level 3) will be provided including narratives, giving qualitative descriptions of the severe episodes.

